## Study purpose and rationale

Over the past 25 years, teen pregnancy rates in the US have dropped primarily due to increased contraception use. Despite this progress, pregnancy risk remains high among adolescent females who use the ED. This risk is largely due to non-use of contraception. Since many of these females lack a primary care provider, the ED is an important place to identify adolescents at highest risk of pregnancy and intervene. However, such an intervention must work efficiently in the busy ED setting, extend the teachable moment between patient and provider, and prolong the motivation for change caused by the ED visit.

In the outpatient setting, text messaging interventions have positively changed health behaviors. In a 2015 systemic review, text messaging interventions were found to be effective when addressing diabetes self-management, weight loss, physical activity, smoking cessation, and medication adherence. For example, texting interventions increased long-term smoking cessation rates compared to controls (Relative Risk=1.7, 95%CI=[1.5-2.0]). Additionally, receivers of text messages promoting weight reduction lost 7 times more weight than controls (-2.6 kg [-3.5,-1.7] vs -0.4 kg [-1.2 to 0.5]).

There is a growing body of evidence that the specific characteristics of text messages influence their effectiveness. In a 2013 meta-analysis, text messaging interventions for health promotion had an overall positive effect size (standardized mean difference (d)=0.33 [0.27, 0.39]); studies that employed both text message *tailoring* and *targeting* had the largest effect (d=0.44 [0.36, 0.52]). Moreover, interventions that applied *personalization* (d=0.44 [0.34, 0.50]) were particularly efficacious. In a separate meta-analysis, texting interventions that included *bidirectionality*, *personalization*, and *tailoring* significantly improved adherence to anti-retroviral therapy (odds ratio (OR)=1.4, [1.2, 1.6]). Lastly, in a 2014 meta-analysis, medication adherence improved in all studies that applied *tailored* or *personalized* messages.

The incorporation of text messaging into health interventions has shown promise in the ED, although few RCTs have been published. In an ED-based RCT, adults who received automated behavioral feedback with texting were 2.4 times (95%CI=1.4, 4.1) more likely to not report any binge drinking in the last 30 days than the control participants. In a small ED-based pilot RCT, young adult females receiving a texting intervention that included feedback increased condom use compared to those who received standard care (53% compared to 20%). A personalized texting program also improved attendance to post-ED follow-up (72.6% vs 62.1%; p=0.045).

There is little data on the use of personalized and interactive text messaging to promote health behaviors among adolescents. However, young women are particularly amenable to text messaging to promote sexual health, perceiving texting as convenient, of minimal cost, and providing a sense of privacy that other forms of health communication do not. In addition, tailored messages are more likely to be read, understood, recalled, rated highly, and perceived as credible. Providing short bursts of information throughout the day, text messaging can provide adolescents with support and in-the-moment, automated advice to assist in smart decision-making.

The specific aim of this study is to test a pregnancy prevention text message program to assess feasibility, acceptability, and effectiveness among sexually active adolescent females in a pediatric emergency department. **This study has two parts.**

**Part 1 is to measure the feasibility, acceptability and potential efficacy of the texting program among a cohort of female adolescent ED patients.**

**Part 2 is to conduct a RCT to test the feasibility, acceptability, and efficacy of the intervention to increase contraception initiation among high risk, adolescent females.**

## APPROACH

### Preliminary Studies

**Proving high rates of teen pregnancy in the ED setting and poor follow up to reproductive preventive services:** In 2012, we found that 20% of our adolescent females (aged 14-19) were expected to become pregnant in the following year, a risk three times the national pregnancy rate and mainly due to non-contraceptive use. Higher risk was associated with frequent ED use and lack of a primary provider. Fifty percent of respondents were receptive to ED-based pregnancy prevention interventions and 25% were interested in starting

contraceptives. In a study published in 2015, we implemented an enhanced method to refer sexually active females from the ED to family planning but found no substantial improvement in follow up.

[figure not shown]
**Understanding barriers to contraceptive use and interest in a mobile health ED-based pregnancy prevention intervention:** (PI: [name]; Funding: 2013 Columbia University Irving Institute CTSA Pilot Grant and Society of Family Planning Pilot Award) In order to build upon our understanding of our target population and how to increase contraceptive use, we conducted a two-part qualitative analysis of females at high pregnancy risk. First, using qualitative data, we developed and published a conceptual model exploring those barriers and enablers affecting their contraceptive use. Subsequently, we determined adolescents' preferences for a pregnancy prevention text messaging intervention, exploring the content, frequency, and timing of conventional (unidirectional and non-interactive) texts. Based on this qualitative data, texts were categorized into three domains: contraceptive education, information about preventive services, and self-efficacy.

**Evaluating a conventional pregnancy prevention text messaging intervention:** We then conducted an ED-based pilot RCT of sexually active females aged 14–19, randomizing patients to receive 3 months of conventional pregnancy prevention texts versus standardized discharge instructions (IRB #AAAM3457). Of the 100 enrolled, feasibility and acceptability were high, with follow-up rates of 88%, 1172/1654 (70.9%) texts successfully delivered, and most (36/41; 87.7%) in the intervention arm wanting future health messages. While there was no signal to suggest a meaningful effect of the intervention for all ages, we identified age group as an effect modifier ( $p=0.02$ ). Overall, younger adolescents (age 14-17 years) initiated contraception more often than older adolescents (age 18-19 years) [34.8% (8/23) versus 11.8% (9/76);  $p=0.01$ ].

**Developing a user-informed, theory-based, personalized, interactive pregnancy prevention texting intervention:** (PI: [name]; Funding: Columbia University KL2 Career Development Grant) In January 2017, we were awarded a 2-year KL2 grant to design and program a personalized and interactive (two-way) pregnancy prevention texting intervention, targeting adolescents at high pregnancy risk using the ED for medical care. There is evidence to suggest that dynamic two-way text messaging interventions, such as those involving alcohol reduction and depression, can guide participants through the process of behavior change. Individually tailored messaging programs provide a sense of personalization and increases personal relevance, which is particularly important for adolescent behavior change.

Over the past year, to design the personalized and interactive texting platform, we have followed the program-planning framework called Intervention Mapping, which is step-wise process of using evidence and theory as a foundation for taking an ecological approach to assessing and intervening in health problems. As seen in Figure 2, we created a Logic Model of Change. This includes our health outcome (to decrease teen pregnancy), the behavioral and environmental outcomes affecting teen pregnancy, and associated performance objectives to change outcomes. Data for this model came from: (1) key stakeholders (e.g. health educators at local high and middle schools and family planning clinics and social workers); (2) our formative quantitative and qualitative work; (3) national and New York State sexual health curricula; (4) evidence-based sexual education guidelines; and (5) an extensive literature review, including logic models from effective teen pregnancy interventions. For the theoretical perspective of our intervention, we chose aspects of the Social Cognitive Theory (SCT), the Unified Theory of Behavior (UTB), and Motivational

**Figure 2. Logic Model of Change to decrease teen pregnancy**

Interviewing (MI). These models are: (1) frequently associated with successful contraception promotion interventions (SCT and MI); (2) specifically address the determinants affecting intention to prevent pregnancy and use birth control (UTB), and (3) augment engagement and a sense of independence (MI). Using these theories and our Logic Model of Change, we developed a curricula of over 20 options for text message algorithms for the present proposal's intervention. (See Attachments for Texting algorithms)

To revise the text message algorithms, we conducted semi-structured interviews with 30 sexually active adolescent female ED patients. (IRB #AAAQ8814) We used key themes to write new and revise existing text messages.

Finally, we also conducted a separate survey of sexually active adolescent female ED patients to inform the design of sexual health comic strips. As part of the intervention, the comic strips include local vernacular to affect personal relevance and social norms. Survey participants were presented with cartoon scenarios and asked to write text messages for the main character. (IRB #AAAR4009) These messages became the text of each comic strip. In an attachment, you will find 5 cartoons that we plan to use in the intervention.

## Part 1: Cohort Study

### Study Design

We will conduct a prospective cohort study on 50 participants recruited in the pediatric ED to assess if the 10-week pregnancy prevention text message program is feasible, acceptable, and potentially effective.

### Study Subjects

The eligibility criteria identify females at high risk of pregnancy who will receive the intervention. Inclusion: (1) age 14-19 years and (2) sexually active with males in the past 3 months. Exclusion: (1) currently using any “effective” form of contraception (as defined by the World Health Organization and includes the Shot, intrauterine device, ring, implantable device, Patch, birth control pills, or sterilization), (2) do not own a mobile phone with text messaging, (3) are pregnant, (4) are too ill for participation per the attending physician, (5) are cognitively impaired, (6) do not live locally (Manhattan or Bronx), (7) do not speak English or (8) does not want to become pregnant in the next year. We will purposively sample 14-17 year old and 18-19 year old patients. Although our population is predominantly Hispanic, we will only enroll English-speaking participants. In our prior work, when we offered English and Spanish text messages, 94% of participants chose English.

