### Recruitment

A member of the research team will identify potentially eligible patients using the electronic medical record (EMR) in the pediatric Emergency Department at New York-Presbyterian Children’s Hospital of New York. Our EMR reveals the age of each patient. The research team member will ask the medical provider caring the patient to confirm eligibility criteria. If a patient is eligible, that provider will privately introduce the study and ask if a research team member can explain it further.

A member of the research team will then privately explain the study in full to the eligible patient in a private location by reviewing the informational form and answering all questions. We used Columbia University IRB-suggested language to design the informational sheet. As part of our information sheet, we will include the language of HIPAA Form B that will include the nature and scope of the PHI to which access is sought and certifications to be made by the researcher.

To ensure the protection or the rights and welfare of the minor, we will put a substitute process in place to verify the minor’s willingness to participate. This will be in the form of a two-person verification (as suggested in IRB correspondence). These 2 people will be the research investigator/ coordinator consenting the patient and the medical provider caring for the patient in the ED (who is involving in the screening process).

Eligible patients will have a choice if they want to sign the informational sheet or verify verbally their agreement to participation. All participants will receive a copy of the informational sheet.

We will explain that we are not responsible for the costs of the texts but do compensate with a gift card. Based on our prior work, the vast majority of our ED adolescent population has unlimited texting on their phones.

We have experience enrolling adolescents into sexual health studies when their parents are present and are able to maintain confidentiality. By explaining the study as a sexual health study aiming to educate adolescents in our community, we are able to discuss the study to both the parent and adolescent. We then talk to the adolescent in private, explain that she was selected because she is at risk of getting pregnant.

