## Study Procedures

Eligible enrolled patients will either text message in the ED will confirm intervention receipt (manual enrollment) or will text RipRoad for enrollment (technological enrollment). This will ensure texting capabilities.

10 participants will receive the 2 month intervention as a beta test. They will receive weekly follow-up calls to qualitatively assess real-life occurrences, such as current sexual activity, change in pregnancy intentions, and perspectives of the messages. Questions will include, “*What about the program is least or most engaging?*” and “*How have your contraceptive choices change because of the texts?*”.

Other probes may include questions about message frequency and time of day. Texts will then be refined and finalized. 40 participants will receive the complete intervention to assess feasibility and acceptability, and potential effectiveness. These participants will not be assessed weekly but rather 3 months after enrollment (week 12).

We expect that approximately 10 of the 50 participants will have technological issues with their phones such as phone disconnections. That is why we have a target accrual of 50 but an actual accrual of 40.

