## Part 2: The pilot randomized control trial

Strategy: We will conduct a pilot RCT of 250 adolescent females at high risk of unintended pregnancy to receive either the 10-week texting program, [name], or standard discharge instructions. *We hypothesize that the texting program will be feasible, acceptable, and increase contraceptive initiation rates (our primary outcome).*

Setting: We will recruit patients from the pediatric ED at New York-Presbyterian Children's Hospital, which cares for over 50,000 patients per year. Patients are predominantly Hispanic, insured, and of low socioeconomic status.

Subjects: The eligibility criteria is the same as Study Part #1. Inclusion: (1) age 14-19 years and (2) sexually active with males in the past 3 months. Exclusion: (1) currently using any "effective" form of contraception (as defined by the World Health Organization and includes the Shot, intrauterine device, ring, implantable device, Patch, birth control pills, or sterilization), (2) do not own a mobile phone with texting, (3) are pregnant, (4) are too ill for participation per the attending physician, (5) are cognitively impaired, (6) do not live locally within the 5 boroughs, Westchester, Rockland, Nassau or Suffolk counties, (7) do not speak English or (8) want to "become pregnant in the next year."

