  - In our prior qualitative interviews, we learned that adolescents receive their health information from unreliable sources, especially on the Internet. We created [www.dr-erica.com](http://www.dr-erica.com) as a one-stop website that contains reliable, medically accurate links to websites such as StayTeen.org and Bedsider.org. Topics include birth control options, local clinics, testimonials, and an introduction to who Dr.Erica is. Many of the links we sent to teens in our texts are on this site. This site contains NO Columbia identifiers, collects NO patient identifiers, and is approved by Columbia University Information Technology.

- (NEW TO THIS MODIFICATION): We will be asking for email addresses for the following two reasons:
  - Disconnected phone numbers: Adolescents often change phone numbers. If RipRoad reports that a phone number has “undelivered” texts, that is usually due to a disconnected phone number. We will email that participant (using the email template attached in Documents) to ask for an updated phone number.
  - Follow up: If a participant does not complete the follow up survey (sent via text as a link), she will be sent an email with the follow-up survey link (using the email template attached in Documents).
- All text messages are attached under Documents.
- Based on preliminary feedback from Study Part 1, we found that many adolescent text questions into the program such as “Where can I get birth control pills?”. Because this program is automated, when questions are received, we send an error message that reads, “Sorry, we do not understand that. If you are answering a question, please reread & try again. If you have general questions, check out [www.dr-erica.com](http://www.dr-erica.com).” Therefore, these questions are never answered by the program. As a solution to this, we have built in “[name] Hours.” This will work in the following manner:
  - Any incoming response (text into the program by a participant) that is 4 or more words will trigger two events:
    - A response text to the participant which reads as follows: “Sorry, I don’t understand your text. But we can answer your questions LIVE during our [name] Hours. You can text privately with a confidential health educator who can answer all your questions! [name] Hours are from 7-8pm. I’ll have her text you this week and let you both connect. In the meanwhile, check out dr-erica.com.”

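### Part 1's pregnancy-intention exclusion is the reverse of Part 2's although the criteria are called the same, and the Part 1 analysis counts 100 participants where 50 are planned

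*Combined protocol and SAP*

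**What the plan says.** **Eligibility.** The Study Subjects section of Part 1 opens: "The eligibility criteria identify females at high risk of pregnancy who will receive the intervention". Its last exclusion is "8) does not want to become pregnant in the next year". The Subjects paragraph of Part 2 states "The eligibility criteria is the same as Study Part #1" and then lists the criteria again. There the last two exclusions run "7) do not speak English or (8) want to", followed by the words for becoming pregnant within a year. Part 1 therefore excludes those who do not want a pregnancy, and Part 2 excludes those who do.

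**Counts.** The Study Design section of Part 1 says "We will conduct a prospective cohort study on 50 participants recruited in the pediatric ED". Study Procedures says "10 participants will receive the 2 month intervention as a beta test" and assigns 40 participants to the complete intervention. The same section then expects about 10 of the 50 to have phone problems, and gives this as the reason for a target accrual of 50 and an actual accrual of 40. The Part 1 Statistical Analysis section covers the first 10 participants and then plans descriptive statistics for 90 more.

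**The concern.** The two versions of exclusion (8) cannot both hold if the criteria are the same. The Part 1 version conflicts with the purpose of the programme. Part 2 describes its population as adolescents at high risk of a pregnancy they do not intend. The section on potential benefits says that females in this emergency department report not wanting to conceive. A literal reading of the Part 1 rule would turn those patients away. The rule is operative text: under Recruitment, the treating provider is asked to confirm the eligibility criteria.

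The counts matter because Part 1 is purely descriptive. Its results are proportions, and a reader needs to know the number of participants behind each one. The plan gives two incompatible cohort sizes and uses 40 for two different groups.

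**Working it through.** **Exclusion (8), side by side**

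| Place | Who is excluded |
|---|---|
| Part 1, Study Subjects | those who do not want a pregnancy in the next year |
| Part 2, Subjects | those who want a pregnancy in the next year |
| Part 2, opening statement on criteria | says the two lists are the same |

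Two places show which direction fits the programme: the reference to unintended pregnancy in the Part 2 strategy, and the statement under potential benefits that females in this department report not wanting to become pregnant. Both agree with the Part 2 wording. The remark about high pregnancy risk in Study Subjects does not separate the two readings, and neither does the Recruitment instruction to "explain that she was selected because she is at risk of getting pregnant". A sexually active patient who uses no effective contraception is at risk of pregnancy whether or not she wants one.

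The documents give no breakdown of screened patients by pregnancy intention, so the share affected by the reversed rule cannot be calculated.

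**Whether Part 1 had begun.** The Part 2 Sources of material section reports preliminary feedback from Part 1, including the example question "Where can I get birth control pills". Participants were therefore already using the programme when this text was written. Correcting the sentence will not by itself show which rule was used.

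**Counts**

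Inputs: 50 (Study Design); 10 and 40 (Study Procedures); 10 and 90 (Statistical Analysis).

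- Study Procedures: 10 + 40 = 50. This reproduces the planned cohort size.
- Statistical Analysis: 10 + 90 = 100, and 100 / 50 = 2. The analysis text implies twice the planned cohort.
- Remainder after the first 10: 50 - 10 = 40, so the 90 is too high by 90 - 40 = 50.

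**Two meanings of 40**

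- Full-programme group: 50 - 10 beta testers = 40.
- Accrual statement: 50 - about 10 with phone problems = about 40.

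The results are equal, but different people are subtracted. The groups coincide only if every phone failure occurs among the beta testers, and the documents do not say that.

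**Which rates are affected.** The Part 1 measures that depend on the number of participants are mainly loss to follow-up, opt-out and contraception initiation. Enrolment is defined as a proportion of those eligible, so its denominator is none of these counts. Technological problems are described by bounced messages, which reads as a rate per message.

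**Residence.** Part 1 limits residence to Manhattan or the Bronx. Part 2 admits all five boroughs and four further counties. The statement that the criteria are the same is therefore inaccurate on a second item.

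**The case against.** The strongest case on the other side is that these are recoverable slips in a descriptive cohort. Part 2 restates exclusion (8) in the direction that makes sense and calls it the same rule, so the intention can be inferred. The 90 appears once, against consistent figures of 50, 10 and 40. Part 1 has no hypothesis test and no power calculation. Since it had already started, rewording changes the record and not the recruitment already done. Most of this stands, and it limits the weight of the point. It does not remove the contradiction: the reversed wording is the Part 1 eligibility list itself, and a reader of the Part 1 results could not tell which rule had been applied.

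A reader might draw stronger conclusions that the documents do not support:

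- *Part 1 recruited the wrong population.* Nothing shows that the literal rule was followed.
- *The Part 1 enrolment rate can no longer inform the trial.* No such use is planned. Part 2 measures its own refusal rate, and its expected accrual of 250 rests on prior emergency department studies.
- *Every Part 1 rate has an unknown denominator.* Enrolment and bounced messages do not use the cohort count. For initiation, those lost to follow-up without evidence in the medical record are already counted as not initiated.
- *The precision of Part 1 is misstated.* Part 1 plans no confidence intervals.
- *The trial's sample size is undermined.* Its 17% comparison rate is attributed to prior data, and none of its sample-size inputs comes from the Part 1 count or from Part 1 exclusion (8).

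**Conclusion.** The plan is wrong as written in two places, and the effect is limited to the descriptive Part 1 cohort. First, Part 1 exclusion (8) is the opposite of the Part 2 criterion it is said to match, and taken literally it excludes the adolescents the programme is for. That it is a drafting slip is an inference from the Part 2 strategy and the benefits section; the size of any effect on recruitment cannot be computed from the documents. Second, the Part 1 analysis implies 100 participants against 50 planned, with 90 where the plan's own split gives 40, and 40 itself has two meanings. The residence difference is minor. No design or power figure of the randomised trial changes. The corrections should be made before Part 1 is reported.

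**What to change.** 1. Reconcile exclusion (8) in the Part 1 Study Subjects section with Part 2, so that wanting a pregnancy in the next year is the exclusion.
2. Check the Part 1 screening records and the baseline pregnancy-intention items, which Sources of material already lists, to confirm which rule was applied. Report the answer with the Part 1 results.
3. In the Part 1 Statistical Analysis section, change 90 to 40 or document where the 90 comes from.
4. Reword the accrual sentence in Part 1 Study Procedures so that 40 refers to one group only. State the denominator for loss to follow-up, opt-out and contraception initiation.
5. In the Part 2 Subjects paragraph, say that the residence criterion differs from Part 1.

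The cost is a few wording corrections, one check of existing records and one line in the Part 1 report. No new data are needed.
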